7.5.2.2 Laboratory Tests for NCI-CTC Toxicity Grading

Laboratory test results for the selected laboratory tests will be graded programmatically using the standardized NCI-CTC toxicity grading criteria (Grade 0, 1, 2, 3, 4) specified in the 10.9 Appendix 9: Standard Toxicity Grading for Laboratory Tests According to National Cancer Institute Common Terminology Criteria for Adverse Events (NCI-CTCAE) v4.0. Shift-from-Week 0 to worst value during entire period will be provided. Note: AEs in this study are graded the investigator using NCI-CTAE Grade (1, 2, 3, 4, 5).

7.5.2.3 Laboratory Tests for Reference Range

Test results for the selected laboratory tests in the table below will be summarized against the reference range indicated. Number and percentage for the Highest/Lowest values of each subject included in pre-specified reference range for select laboratory during entire period will be provided.

Select Laboratory Variables and Corresponding Reference Ranges

Select Laboratory Variable	Reference Range	Highest/Lowest	Note
Aspartate Aminotransferase (AST)	>= 1 × ULN to < 2 × ULN >= 2 × ULN to < 3 × ULN >= 3 × ULN	Highest	
Alanine Aminotransferase (ALT)	>= 1 × ULN to < 2 × ULN >= 2 × ULN to < 3 × ULN >= 3 × ULN	Highest	
Alkaline Phosphatase (ALP)	> 2 × ULN to <= 3 × ULN > 3 × ULN to <= 5 × ULN > 5 × ULN	Highest	
Total Bilirubin	>1.5× ULN	Highest	
Total Bilirubin	>= 1 × ULN to < 2 × ULN >= 2 × ULN to < 3 × ULN >= 3 × ULN	Highest	
Low-Density Lipoprotein (LDL)	> 160 mg/dL	Highest	
Low-Density Lipoprotein (LDL) (maximum value)	< 100 mg/dL 100 to < 130 mg/dL 130 to < 160 mg/dL 160 to < 190 mg/dL >= 190 mg/dL	Highest	
Hemoglobin (HGB)	>=8.0 to < 10.0 g/dL < 8.0 g/dL	Lowest	
Hemoglobin (HGB)	>= (Week 0 value -2) to <(Week 0 value -1) g/dL <(Week 0 value -2) g/dL	Lowest	
Hemoglobin (HGB)	 Mild to Moderate: decrease from Week 0 value >= 1 to <= 2 g/dL, Severe: decrease from Week 0 value >2 to <3 g/dL or absolute value >7 and <8 g/dL, Potentially Life Threatening: decrease from Week 0 value >= 3 or absolute value <= 7 g/dL 	Lowest	
Creatine Phosphokinase (CPK)	> 500 to <= 2,000 U/L > 2,000 U/L	Highest	Based on "CPK Monitoring" in protocol
Creatine Phosphokinase (CPK)	> 5 × Week 0 value	Highest	Based on "CPK Monitoring" in protocol

Select Laboratory Variable	Reference Range	Highest/Lowest	Note
Creatine Phosphokinase	$> 2 \times ULN \text{ to} \le 5 \times ULN$	Highest	Based on "CPK
(CPK)	$>$ 5 × ULN to \leq 10 × ULN		Monitoring" in
	> 10 × ULN		protocol
Creatinine	$> 1.5 \times \text{Week 0 value to} \le 3.0$	Highest	
	×Week 0 value		
	$> 3.0 \times \text{Week 0 value}$		
Absolute Neutrophil Count	$>= 1,500 \text{ to} < 2,000 / \text{mm}^3$	Lowest	Based on
(ANC)	$>= 500 \text{ to} < 1,500 / \text{mm}^3$		"OMERACT
	< 500 / mm^3		criteria"
Lymphocytes	>= 200 to < 500 / uL	Lowest	
	< 200 /uL		
Lymphocytes	$>= 1,500 \text{ to} < 2,000 / \text{mm}^3$	Lowest	Based on
	$>= 500 \text{ to} < 1,500 / \text{mm}^3$		"OMERACT
	< 500 / mm^3		criteria"
Platelets	$>= 2 \times 10^4 \text{ to} < 5 \times 10^4 \text{ /uL}$	Lowest	
	$< 2 \times 10^4 / \text{uL}$		
Platelets	> 600,000 /uL	Highest	
ULN = Upper Limit Normal			

7.5.2.4 Liver Abnormalities

Each categories are mutually exclusive.

The following potentially clinically significant criteria in liver function tests for Alkaline Phosphatase (ALP), Alanine Transaminase (ALT), total bilirubin, Aspartate Transaminase (AST) and their combination are defined. The subject's highest value during the investigational period will be used.

Parameter	Criteria
ALT	> 3xULN
	> 5xULN
	> 10xULN
	> 20xULN
AST	> 3xULN
	> 5xULN
	> 10xULN
	> 20xULN
ALT or AST	> 3xULN

> 8xULN

Total Bilirubin > 2xULN

ALP > 1.5xULN

ALT and/or AST OR Total Bilirubin(*) (ALT and/or AST \geq 3xULN) or

total bilirubin > 2xULN

ALT and/or AST AND Total Bilirubin^(*) (ALT and/or AST > 3xULN) and total bilirubin

> 2xULN

The number and percentage of subjects with potentially clinically significant values in liver function tests during the investigational period will be presented.

Additionally, confirmed liver abnormities will be characterized as moderate and marked, as follow:

Moderate: ALT or AST $> 3 \times ULN$ OR Total Bilirubin $> 2 \times ULN$.

Marked: ALT or AST $> 3 \times ULN$ AND Total Bilirubin $> 2 \times ULN$.

Number and percentage of subjects in each category at each scheduled visit will be summarized. These combinations of elevated values are based on measured value within the same sample.

7.5.2.5 Liver Functions Plots

A matrix scatter plot of liver function test will be plotted showing the maximum ALT, AST, ALP and total bilirubin during the study period crossed against each other. Different dots will be used for preceding studies.

7.5.3 Vital Signs

Raw values and changes from Week 0 at each scheduled visit will be summarized using descriptive statistics.

7.5.4 Electrocardiograms (ECGs)

<12-lead ECG>

• Raw values (categorical) and changes from Week 0 (shift from Week 0) will be summarized, and the summaries will include number and percentage of subjects with normal, not clinically significant abnormal and clinically significant abnormal 12 lead ECG findings.

^(*) Combination of values measured within same sample

7.5.5 Chest radiography

Chest radiography will be provided as a subject listing only.

7.5.6 Pregnancies

Pregnancies will be provided as a subject listing only.

7.6 Analysis of PK

Refer to PK SAP.

7.7 Analysis of PD

[Analysis Set: PDAS]

For subjects who shift from RAJ3, as described in 7.5.2, harmonization for lymphocytes subset variables among each region (Japan, Korea, Taiwan) was reported to be difficult and therefore, raw values and changes from baseline of preceding study will be summarized by Study Region (Japan, Korea, Taiwan), using descriptive statistics. For CD3, CD8, CD4, CD19, CD4/CD8 ratio, (CD16 or CD56)+, CD16+ and CD56+, CD16- and CD56+, CD16- and CD56-, count values (cells/uL) will be summarized by whole population for exploratory analysis.

1. Japan

- CD3+/Lymphocytes (%), CD3+ (cells/uL)
- o CD8+/Lymphocytes (%), CD8+ (cells/uL)
- CD4+/Lymphocytes (%), CD4+ (cells/uL)
- CD19+/Lymphocytes (%), CD19+ (cells/uL)
- CD4/CD8 Ratio
- (CD16 or CD56)+/Lymphocytes (%), (CD16 or CD56)+ (cells/uL)
- o (CD16+ and CD56+)/CD3- (%), CD16+ and CD56+ (cells/uL)
- o (CD16- and CD56+)/CD3- (%), CD16- and CD56+ (cells/uL)
- o (CD16+ and CD56-)/CD3- (%), CD16+ and CD56- (cells/uL)
- o (CD16- and CD56-)/CD3- (%), CD16- and CD56- (cells/uL)
- CD56 bright/CD3- (%), CD56 bright (cells/uL)
- o CD56 dim/CD3- (%), CD56 dim (cells/uL)

2. Korea

- CD3+/Lymphocytes (%), CD3 (cells/uL)
- o (CD3+ and CD8+)/CD3+ (%), CD3+ and CD8+ (cells/uL)
- o (CD3+ and CD4+)/CD3+ (%), CD3+ and CD4+ (cells/uL)
- o (CD16 or CD56)+/CD3- (%), (CD16 or CD56)+ (cells/uL)
- o CD19+/CD3- (%), CD19+ (cells/uL)
- o CD4/CD8 Ratio
- o (CD16+ and CD56+)/CD3- (%), CD16+ and CD56+ (cells/uL)
- o (CD16- and CD56+)/CD3- (%), CD16- and CD56+ (cells/uL)
- o (CD16+ and CD56-)/CD3- (%), CD16+ and CD56- (cells/uL)
- o (CD16- and CD56-)/CD3- (%), CD16- and CD56- (cells/uL)

3. Taiwan

- o CD3+/Lymphocytes (%), CD3 (cells/uL)
- o (CD3+ and CD8+)/Lymphocytes (%), CD3+ and CD8+ (cells/uL)
- o (CD3+ and CD4+)/Lymphocytes (%), CD3+ and CD4+ (cells/uL)
- o (CD16 or CD56)+/Lymphocytes (%), (CD16 or CD56)+ (cells/uL)
- o CD19+/Lymphocytes (%), CD19+ (cells/uL)
- o CD4/CD8 Ratio
- o (CD16+ and CD56+)/Lymphocytes (%), CD16+ and CD56+ (cells/uL)
- o (CD16- and CD56+)/Lymphocytes (%), CD16- and CD56+ (cells/uL)
- o (CD16+ and CD56-)/Lymphocytes (%), CD16+ and CD56- (cells/uL)
- o (CD16- and CD56-)/Lymphocytes (%), CD16- and CD56- (cells/uL)

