Administration of ASP015K 100 mg BID had no effect on the pharmacokinetic profile of MTX in patients with RA or the MMF metabolites MPA and MPAG in healthy volunteers. ASP015K 60 mg and 100 mg BID did increase tacrolimus levels in whole blood following oral administration of tacrolimus 5 mg, but not when tacrolimus was administered as a 1 mg intravenous dose. Concomitant use of ASP015K elevated the plasma midazolam concentrations after a single oral dose of midazolam 3 mg. It also raised the plasma rosuvastatin levels following a single oral dose of rosuvastatin 10 mg. However, steady-state pharmacokinetics of ASP015K were not significantly impacted by MTX 15 to 25 mg, MMF 1 g, midazolam 3 mg, oral tacrolimus 5 mg, or intravenous tacrolimus 1 mg doses.

In Study 015K-CL-PS01 that enrolled patients with psoriasis, the administration of ASP015K 10 to 100 mg BID elevated ASP015K exposure ( $C_{max}$ ,  $AUC_{last}$ , and  $AUC_{6h}$ ) in a dose-dependent manner. The median  $t_{max}$  values were in the range of approximately 1.0 to 1.8 hours. STAT5 phosphorylation and JAK3 activity were inhibited in a dose-dependent manner. Although no consistent trends were noted for the absolute lymphocyte count, a slight dose-dependent decreasing trend was noted for the proportions and absolute counts of NK and B cells.

In Study 015K-CL-RAJ1 of Japanese patients with RA, matrix metalloproteinase 3 levels decreased in a dose-dependent manner following the administration of ASP015K 25 to 150 mg QD. Although no consistent trends were noted for the absolute lymphocyte count, NK cell counts decreased and B cell counts increased in a dose-dependent manner.

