6.4 Pharmacodynamic Variables

- Change from baseline for following variables in lymphocyte subset assays
- 1. Japan
 - o CD3+/Lymphocytes (%), CD3+ (cells/uL)
 - o CD8+/Lymphocytes (%), CD8+ (cells/uL)

- o CD4+/Lymphocytes (%), CD4+ (cells/uL)
- CD19+/Lymphocytes (%), CD19+ (cells/uL)
- CD4/CD8 Ratio
- o (CD16 or CD56)+/Lymphocytes (%), (CD16 or CD56)+ (cells/uL)
- (CD16+ and CD56+)/CD3- (%), CD16+ and CD56+ (cells/uL)
- (CD16- and CD56+)/CD3- (%), CD16- and CD56+ (cells/uL)
- (CD16+ and CD56-)/CD3- (%), CD16+ and CD56- (cells/uL)
- o (CD16- and CD56-)/CD3- (%), CD16- and CD56- (cells/uL)
- CD56 bright/CD3- (%), CD56 bright (cells/uL)
- o CD56 dim/CD3- (%), CD56 dim (cells/uL)

2. Korea

- o CD3+/Lymphocytes (%), CD3 (cells/uL)
- o (CD3+ and CD8+)/CD3+ (%), CD3+ and CD8+ (cells/uL)
- o (CD3+ and CD4+)/CD3+ (%), CD3+ and CD4+ (cells/uL)
- o (CD16 or CD56)+/CD3- (%), (CD16 or CD56)+ (cells/uL)
- o CD19+/CD3- (%), CD19+ (cells/uL)
- o CD4/CD8 Ratio
- o (CD16+ and CD56+)/CD3- (%), CD16+ and CD56+ (cells/uL)
- o (CD16- and CD56+)/CD3- (%), CD16- and CD56+ (cells/uL)
- o (CD16+ and CD56-)/CD3- (%), CD16+ and CD56- (cells/uL)
- o (CD16- and CD56-)/CD3- (%), CD16- and CD56- (cells/uL)

3. Taiwan

- o CD3+/Lymphocytes (%), CD3 (cells/uL)
- o (CD3+ and CD8+)/Lymphocytes (%), CD3+ and CD8+ (cells/uL)
- (CD3+ and CD4+)/Lymphocytes (%), CD3+ and CD4+ (cells/uL)
- (CD16 or CD56)+/Lymphocytes (%), (CD16 or CD56)+ (cells/uL)
- o CD19+/Lymphocytes (%), CD19+ (cells/uL)
- o CD4/CD8 Ratio
- (CD16+ and CD56+)/Lymphocytes (%), CD16+ and CD56+ (cells/uL)
- o (CD16- and CD56+)/Lymphocytes (%), CD16- and CD56+ (cells/uL)
- o (CD16+ and CD56-)/Lymphocytes (%), CD16+ and CD56- (cells/uL)

o (CD16- and CD56-)/Lymphocytes (%), CD16- and CD56- (cells/uL)

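### SAP 7.7 pools CD8 and CD4 counts over all regions, although Japan lists all CD8+ and CD4+ cells and Korea and Taiwan list only those that are also CD3+

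*SAP*

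**What the plan says.** SAP 7.7 states that "harmonization for lymphocytes subset variables among each region (Japan, Korea, Taiwan) was reported to be difficult" and for that reason summarises raw values and changes from the preceding study's baseline by Study Region. It then lists the parameters to be pooled, "For CD3, CD8, CD4, CD19, CD4/CD8 ratio, (CD16 or CD56)+, CD16+ and CD56+, CD16- and CD56+, CD16- and CD56-, count values (cells/uL", and says that these "count values (cells/uL) will be summarized by whole population for exploratory analysis". Only counts are pooled, not percentages.

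The regional lists, given in both SAP 6.4 and 7.7, define the counts. The quoted runs below are cut at a bracket.

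- Japan, CD8: "CD8+/Lymphocytes (%), CD8+ (cells/uL"
- Korea, CD8: "CD3+ and CD8+)/CD3+ (%), CD3+ and CD8+ (cells/uL"
- Taiwan, CD8: "CD3+ and CD8+)/Lymphocytes (%), CD3+ and CD8+ (cells/uL"

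CD4 follows the same pattern: CD4+ in Japan, CD3+ and CD4+ in Korea and Taiwan. CD4/CD8 Ratio appears under one label in all three lists, without a formula. Protocol 2.3.3 and 5.3.2.1 name only the markers, so they do not settle which definition is meant. Protocol 7.6.1 sets the default that PD data are tallied by preceding study and for the entire RAJ2 population, unless otherwise specified.

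**The concern.** Using counts removes the problem that the percentages have different bases. It does not change which cells are counted. CD8+ cells include any that lack CD3; CD3+CD8+ cells by definition do not. For the same subject the Japanese count can only be equal to or higher than the Korean or Taiwanese one. A pooled row labelled CD8 or CD4 mixes the two definitions, and nothing in SAP 7.7 tells the reader so.

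A reader of the pooled table would take each row as one quantity followed over time. If the share of Japanese subjects differs between visits, the raw mean can move although no subject has changed.

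**Working it through.** There is no plan figure to reproduce, because the summary is descriptive. The first check sets the nine pooled parameters side by side, using the lists in SAP 7.7.

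| Pooled row | Count: Japan | Count: Korea, Taiwan | Percentage base: Japan / Korea / Taiwan |
|---|---|---|---|
| CD3 | CD3+ | CD3 (listed with CD3+ as the percentage) | lymphocytes / lymphocytes / lymphocytes |
| CD8 | CD8+ | CD3+ and CD8+ | lymphocytes / CD3+ / lymphocytes |
| CD4 | CD4+ | CD3+ and CD4+ | lymphocytes / CD3+ / lymphocytes |
| CD19 | CD19+ | CD19+ | lymphocytes / CD3- / lymphocytes |
| CD4/CD8 | ratio, no formula | ratio, no formula | not applicable |
| (CD16 or CD56)+ | same label | same label | lymphocytes / CD3- / lymphocytes |
| CD16+ and CD56+ | same label | same label | CD3- / CD3- / lymphocytes |
| CD16- and CD56+ | same label | same label | CD3- / CD3- / lymphocytes |
| CD16- and CD56- | same label | same label | CD3- / CD3- / lymphocytes |

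Two rows (CD8, CD4) have count labels that differ by region. One (CD4/CD8) depends on an unstated formula. Six have matching count labels: 2 + 1 + 6 = 9.

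**Size for CD8, on assumptions.** Let d be the proportion by which total CD8+ exceeds CD3+CD8+, and w the share of subjects from Korea and Taiwan. The documents give neither. Assume also that the true CD3+CD8+ mean is the same in all regions. The pooled mean divided by the CD3+CD8+ mean is then 1 + (1 - w) x d.

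- d = 5%, w = 50%: 0.50 x 5% = 2.5% excess
- d = 20%, w = 30%: 0.70 x 20% = 14% excess
- d = 40%, w = 10%: 0.90 x 40% = 36% excess

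**Movement from mix alone.** If w rose from 10% to 50% between two visits, with no change in any subject:

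- d = 5%: 1.025 / 1.045 = 0.981, an apparent fall of 1.9%
- d = 20%: 1.10 / 1.18 = 0.932, an apparent fall of 6.8%
- d = 40%: 1.20 / 1.36 = 0.882, an apparent fall of 11.8%

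A fall in w would give an apparent rise.

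**Can the mix change?** The documents give two reasons why it may. Protocol 2.2.1 limits the Japanese part to at most 6 months after Japanese approval, while Korea and Taiwan continue. RAJ1 was run in Japan (Protocol 1.2.4), and the version 1.3 schedule in Protocol Appendix 7, under which RAJ1 subjects entered, has no lymphocyte-subset row. Early PD visits may therefore lack these subjects. Neither reason fixes the direction or size of the shift at a given visit.

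**CD4/CD8.** If the ratio is formed from the listed counts and e is the CD4 counterpart of d, the Japanese ratio equals the CD3+ ratio times (1 + e)/(1 + d). Its direction depends on two unknowns, so no size is given.

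**The case against.** The SAP is open about the problem. It reports that harmonisation was difficult, makes the regional summaries the main ones, keeps percentages out of the pooling and labels the pooled table exploratory. SAP 7.8.2 repeats the PD analysis by region, and Protocol 7.6.1 asks for a whole-population tally by default. All of this stands and limits the weight of the point. It does not cure it: assays of one parameter that could not be harmonised are a different matter from two parameters under one row name.

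Three stronger readings are tempting, and the documents do not support them.

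1. *A reader might infer that the CD16/CD56 counts are also mismatched*, because Taiwan writes "CD16+ and CD56+)/Lymphocytes (%), CD16+ and CD56+ (cells/uL" where Japan and Korea use CD3- cells as the percentage base. The pooled counts, however, carry the same label in all three regions, and the differing bases belong to percentages that are not pooled. The SAP states no gate behind any count. (CD16 or CD56)+ and CD19 show the same pattern of label and base, so removing one and keeping the other would be inconsistent.
2. *A reader might infer that pooling would pass off NK-cell loss as a CD8 effect*, since Protocol 1.2.2.2 reports for RAJ1 that "NK cell counts decreased and B cell counts increased in a dose-dependent manner". That needs some NK cells to carry CD8, for which the documents give no figure. The effect would also remain in the Japan-only table, and pooling with CD3+ counts would dilute it.
3. *A reader might infer that pooled changes from baseline are biased by the same amount as the levels.* If each subject stays within one regional definition, a constant offset cancels. Only a change in the CD3-negative part would remain.

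Nor do RAJ1 and RAJ4 being Japanese studies by themselves make the mix change between visits; the argument rests on the two reasons given in the working.

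**Conclusion.** The point holds for CD8 and CD4 on the face of SAP 6.4 and 7.7, and for CD4/CD8 if the ratio is formed from those counts. These rows of the whole-population summary do not describe one parameter, and their raw by-visit means can move with regional mix.

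The range of 2.5% to 36% for the pooled CD8 level rests wholly on assumed values of d and w and on equal CD3+CD8+ means across regions. It shows only that the effect need not be trivial. Within RAJ4, which is Japanese only, and RAJ1, which was run in Japan, there is one definition, so the issue concerns the RAJ3 and RAJ2 totals.

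Whether CD19 and the CD16/CD56 counts share a parent gate across regions is a query to the sponsor and not a demonstrated error. Severity is minor: one exploratory descriptive table, with no test attached.

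**What to change.** In SAP 7.7, take CD8, CD4 and the CD4/CD8 ratio off the list for the whole-population summary and report them by Study Region only. Korean and Taiwanese CD3+CD8+ and CD3+CD4+ counts may be combined with each other. Keep CD3, CD19 and the four CD16/CD56 counts in the pooled summary. Record the change as a stated exception to the default in Protocol 7.6.1, which allows one.

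Ask the sponsor for the parent gate behind the CD19 and CD16/CD56 counts in each region, and for the CD4/CD8 formula. If the ratio proves to be built from one definition everywhere, it can return to the pooled list.

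The cost is three rows of an exploratory table and the loss of an all-region figure for those parameters. No new data are needed, and the regional tables are already planned.

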7.8 Subgroups of Interest

7.8.1 Subgroup analysis of the selected efficacy endpoint (ACR20-CRP) and treatment emergent adverse events

The selected efficacy variable (ACR20-CRP) and TEAEs will be summarized for the subgroups defined on the basis of the categorized variables listed below:

- Sex (Male, Female,)
- \circ Age Group at Week 0 (< 65 years, >= 65 years)
- Prior Anti-TNF DMARD Use in preceding study (User, Non-user)
- Prior Biologic DMARD-IR in preceding study (No. Yes)

- Duration of RA (years) in preceding study (< 5 years, >= 5 years)
- Number of Prior DMARDs Used in preceding study $(0, 1, 2, \ge 3)$
- \circ Number of Prior Biologic DMARDs Used in preceding study $(0, 1, 2, \ge 3)$
- MTX Dose (mg/week) at Week 0 (None, 0 <- 8 mg/week, 8 <- 12 mg/week, > 12 mg/week)
- Concomitant Steroid at Week 0 (No, Yes)
- \circ Prednisone Dose (mg/day) at Week 0 (None, 0 <- 5 mg/day, > 5 mg/day)
- Concomitant non-Biologic DMARD Use at Week 0 (No, Yes)
- Study Region (Japan, Korea, Taiwan)
- Baseline DAS28-CRP in preceding study (<= 3.2, 3.2<-5.1, > 5.1), efficacy analyses only
- Baseline DAS28-ESR in preceding study (<= 3.2, 3.2<-5.1, > 5.1), efficacy analyses only
- Baseline CRP in preceding study (< 1.0, >= 1.0), efficacy analyses only
- Concomitant DMARD category at Week 0 (MTX, DMARD except for MTX only, None)
- Body Weight (kg) at Week 0 (<- 40 kg, 40 kg <- 60 kg, 60 kg <- 80 kg, > 80 kg)
- Maximum Dose of Study Drug (50 mg, 100 mg, 150 mg)

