#### **5.1.2 Increase or Reduction in Dose of the Study Drugs**

The dose increase/reduction of study drugs is allowed only when the following criteria are met. For subjects who have been receiving ASP015K at a dose of 50 mg/day in Japan, the dose will be increased to 100 mg/day after approval in Japan. Any subjects for whom the dose cannot be increased should be withdrawn from the study.

[The increase in dose from 50 mg/day to 100 mg/day]

- CONFIDENTIAL -

Japan: For subjects who have been receiving ASP015K at a dose of 50 mg/day in Japan, the dose will be increased to 100 mg/day after approval. Any subjects for whom the dose cannot be increased should be withdrawn from the study.

Korea and Taiwan: When the investigator or sub-investigator judges that there is no safety problem in the subject, the dose may be increased from 50 mg to 100 mg.

[The increase in dose from 100 mg/day to 150 mg/day]

The dose may be increased from 100 mg to 150 mg at the time point when the following 2 conditions are met:

- 1) The subject has taken ASP015K 100 mg for at least 4 weeks, and the DAS28-ESR score is 3.2 or higher (moderate disease activity or high disease activity) on the study visit days.
- 2) When the investigator or sub-investigator judges there to be no problem with safety for the subject in the assessment performed on the study visit day on which the DAS28-ESR score of 3.2 or higher was exhibited.

[The reduction in dose from 100/day mg or 150 mg/day to 50 mg/day]

Japan: After the NDA approval in Japan, dose reduction for the study drugs is not allowed.

Korea and Taiwan: After the dose increase, the dose may be reduced from 100 mg/day or 150 mg/day to 50 mg/day at the discretion of the investigator or sub-investigator.

The investigator or sub-investigator will decide whether or not to reduce the dosage on the basis of the following criterion.

- If an AE with NCI-CTCAE grade classification of Grade 2 or higher has developed.

A dose increase after a dose reduction and a dose reduction after a dose increase are allowed according to the above criteria.

If the dose of study drug has been increased or reduced, the investigator or sub-investigator should record this information in the CRF.

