7.3.1 Exposure

[Analysis Set: SAF]

Duration of exposure during RAJ2 will be summarized in two ways.

- Descriptive statistics will be presented
- Exposure time for overall period will be categorized according to the following categories:
 - \circ 0 1 month
 - \circ 1 <- 3 months
 - \circ 3 <- 6 months
 - 6 <- 12 months
 - 12 <- 24 months
 - o 24 <- 36 months
 - 36 <- 48 months
 - 48 <- 60 months
 - o 60 <- 72 months
 - 72 <- 84 months
 - o 84 months <

Counts and percentages of subjects in each category will be summarized.

In addition to this, the following information on drug exposure will be presented:

- Number and percent of subject with dose increase/ dose decrease/ drug suspension/ drug interruption
- Number of experience for dose increase/ dose decrease/ drug suspension/ drug interruption per subject
- Duration from First Study Drug Taken up to First Dose Change to ASP015K 100 mg (from RAJ1) or 150 mg (from RAJ3/RAJ4)
- Maximum Dose of Study Drug (ASP015K 50 mg/ 100 mg/ 150 mg)

The following Kaplan-Meier plot of time-to-event from initial dose will be constructed.

		Event	Censor
Time to changing initial 50mg	RAJ1	Dose increase Discontinuation	Study Completion
Time to changing initial 100mg	RAJ3/4	Dose increase Dose decrease Discontinuation	Study Completion
Time to dose increasing initial 100mg	RAJ3/4	Dose increase	Study Completion Discontinuation Dose decrease
Time to dose decrease initial 100mg	RAJ3/4	Dose decrease	Study Completion Discontinuation Dose increase

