7.4.3 Analysis of Efficacy in Initial/Maximum Dose Level

The selected efficacy variables (ACR20-CRP and DAS28-CRP) are summarized by preceding study. In Initial dose analysis, data obtained after changing initial dose at RAJ2 (50mg for subjects from RAJ1, 100mg for subjects from RAJ3/4) will not be used for efficacy analyses.

- Categorical variables at each visit will be summarized.
- For continuous variables, raw value and change from baseline of preceding study at each visit will be summarized by descriptive statistics.

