7.4.5 Subgroup Analysis

In order to evaluate homogeneity of treatment effects across subjects with different demographic and baseline characteristics, subgroup analysis of the efficacy variables will be performed, respectively. The subgroups in Section 7.8 will be analyzed.

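### ACR20 by maximum dose reached is conditioned on disease activity at 100 mg, so it is biased against 150 mg and cannot be read as a dose comparison

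*SAP*

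**What the plan says.** SAP 7.8.1 opens its list with "The selected efficacy variable (ACR20-CRP) and TEAEs will be summarized for the subgroups defined on the basis of the categorized variables listed below". The list includes "Maximum Dose of Study Drug (50 mg, 100 mg, 150 mg"). Three other entries are marked for efficacy only, but this one carries no restriction, so it applies to ACR20-CRP as well as TEAEs. SAP 7.3.1 treats the same variable as drug exposure: "Maximum Dose of Study Drug (ASP015K 50 mg/ 100 mg/ 150 mg").

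SAP 7.4.5 gives the purpose of the efficacy subgroups as checking "homogeneity of treatment effects across subjects with different demographic and baseline characteristics".

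SAP 7.4.3 is headed "Analysis of Efficacy in Initial/Maximum Dose Level". It covers ACR20-CRP and DAS28-CRP by preceding study. It says which data are dropped for the initial-dose analysis and gives no rule for a maximum-dose analysis.

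Protocol 5.1.2 sets the rule for the increase: "The dose may be increased from 100 mg to 150 mg at the time point when the following 2 conditions are met". The first condition is "The subject has taken ASP015K 100 mg for at least 4 weeks, and the DAS28-ESR score is 3.2 or higher"; the second is that the investigator sees no safety problem. The Synopsis gives lack of efficacy as the reason for an increase.

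SAP Appendix 1, item 1.5.1, which lists the ACR20 subgroups, does not include maximum dose. Items 1.3 and 10.3, which correspond to 7.4.3, describe an analysis by each dose level.

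**The concern.** A baseline subgroup is fixed before the outcome is seen. Maximum dose is not: it depends on how the subject did on 100 mg. DAS28-ESR (Protocol 5.3.1.5) and ACR20 (SAP 6.1.1) both use tender joints, swollen joints and the subject's global assessment, so the trigger for 150 mg is related to the response being tabulated.

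Two things follow. Subjects who do well on 100 mg tend to stay in the 100 mg column, and those with active disease tend to move to the 150 mg column. And because categorical efficacy variables are tabulated at each visit (SAP 7.4.1), the 150 mg column includes visits at which those subjects were still taking 100 mg.

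A reader given ACR20 in dose columns will compare them. Neither 7.4.3 nor 7.8.1 warns against this, and the wrong conclusion about 150 mg could be drawn.

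**Working it through.** The plan gives no figure for this comparison, so there is nothing to reproduce. The check asks what the table would show if 150 mg were truly better by a known amount.

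**Inputs from the documents.** The randomised RAJ1 ACR20 rates at Week 12 are 54.5% on 100 mg and 65.5% on 150 mg (Protocol 1.2.4), a difference of 11.0 points. They serve only as a calibration and are not RAJ2 rates.

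**Assumptions (not in the documents).** ACR20 non-responders on 100 mg escalate with probability eN from 0.5 to 0.9. Responders escalate with probability eR, which is 0.75, 0.5 or 0.25 times eN. Responders keep their response after the increase.

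**Formulas.** Let p = 0.545. For 150 mg given to everyone to yield 65.5%, it must convert a share c of non-responders:

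c = (0.655 - 0.545) / (1 - 0.545) = 0.242

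Rate in the 150 mg group = [p·eR + (1-p)·eN·c] / [p·eR + (1-p)·eN]

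Rate in the 100 mg group = p(1-eR) / [p(1-eR) + (1-p)(1-eN)]

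**Example: eN = 0.7, eR = 0.35.**

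- 150 mg group: (0.19075 + 0.3185 × 0.242) / (0.19075 + 0.3185) = 52.6%
- 100 mg group: 0.35425 / (0.35425 + 0.1365) = 72.2%
- Difference: -19.6 points, where the truth is +11.0
- With c = 0 (no benefit at all), the 150 mg group would show 0.19075 / 0.50925 = 37.5%. Selection alone then produces a gap of about -35 points.

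**Grid.** Differences come from unrounded values; the truth is +11.0 throughout.

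| eN | eR | Maximum 150 mg | Maximum 100 mg | Difference (points) |
|---|---|---|---|---|
| 0.5 | 0.375 | 60.1% | 60.0% | +0.1 |
| 0.5 | 0.25 | 52.6% | 64.2% | -11.7 |
| 0.5 | 0.125 | 41.6% | 67.7% | -26.1 |
| 0.7 | 0.525 | 60.1% | 65.5% | -5.4 |
| 0.7 | 0.35 | 52.6% | 72.2% | -19.6 |
| 0.7 | 0.175 | 41.6% | 76.7% | -35.1 |
| 0.9 | 0.675 | 60.1% | 79.6% | -19.5 |
| 0.9 | 0.45 | 52.6% | 86.8% | -34.2 |
| 0.9 | 0.225 | 41.6% | 90.3% | -48.6 |

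With eR = eN there is no selection and the table returns the true +11.0.

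**Visits before the increase.** While still on 100 mg, subjects later classed as 150 mg have an ACR20 rate of p·eR / [p·eR + (1-p)·eN]. This is 47%, 38% and 23% for eR at 0.75, 0.5 and 0.25 times eN.

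**Second model.** ACR20 and DAS28-ESR were given correlated latent normal scores, with 40% or 60% of subjects above the trigger and 50% or 90% of those escalating. The differences were +11 points at correlation 0, -6.6 to +0.8 at 0.3, -19.2 to -6.7 at 0.5, and -34.0 to -14.2 at 0.7.

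**Discontinuation.** Non-responders who stop on 100 mg before escalating stay in the 100 mg group and lower its rate. With eN = 0.7 and eR = 0.175, early loss of 40% of non-responders gives 49.4% against 63.0%; loss of 60% gives 56.6% against 57.9%.

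**The case against.** The best defence has four parts.

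First, the trigger is not ACR20 non-response. It is an absolute DAS28-ESR level at a visit, with no persistence required, and the increase is optional. ACR20 is a 20% improvement from the preceding-study baseline, so an ACR20 responder can qualify. This stands and limits how strong the selection is.

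Second, efficacy is descriptive, no hypothesis is tested (Appendix 1), and no objective compares doses. That is true, but it does not stop dose columns from being read as a dose comparison.

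Third, other analyses look at dose more carefully. The initial-dose analysis in 7.4.3 drops data after a dose change, and 7.4.4 aligns results to the first increase. Both are useful, but neither corrects the 7.8.1 table. Section 7.4.4 has the opposite risk: subjects enter it after a high DAS28, so regression to the mean could favour the higher dose.

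Fourth, SAP 7.4 refers to Appendix 1 for the efficacy details, and item 1.5.1 omits maximum dose. If the appendix governs, the ACR20 table is not produced. But item 1.5.1 also omits body weight, the neighbouring entry in 7.8.1, so the omission may be an oversight. As written, the two places disagree.

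**Conclusion.** The point holds as a bias with a known direction and an uncertain size. ACR20 by maximum dose is conditioned on disease activity at 100 mg and is not a baseline subgroup of the kind 7.4.5 describes. It is biased against 150 mg. If the truth is +11 points, the table may show about -20 to -49 points under moderate to strong selection (eN 0.7 with eR 0.35, up to eN 0.9 with eR 0.225), about -12 points with lower uptake (eN 0.5, eR 0.25), and about zero when selection is weak. All selection inputs are assumed.

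The documents do not support three stronger readings that a reader might infer:

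- *That 150 mg is certain to look worse.* Weak correlation, low uptake of the increase, or many non-responders stopping on 100 mg can bring the gap to about zero. A true benefit would still be hidden.
- *That the 150 mg group consists of non-responders by rule.* It is enriched for subjects not in low disease activity; ACR20 responders can be in it.
- *That a false inverse dose-response extends to DAS28-CRP and to 50 versus 100 mg.* Section 7.8.1 covers only ACR20-CRP and TEAEs, and DAS28-CRP enters only through an undefined word in the 7.4.3 heading. The move from 50 to 100 mg has mixed causes: a DAS28-ESR trigger under protocol version 1.3 (Protocol Appendix 7), later a default increase with exceptions (Protocol 2.2.2), and in Japan a required increase after approval (Protocol 5.1.2).

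**What to change.** - In SAP 7.8.1, restrict maximum dose of study drug to TEAEs. This agrees with Appendix 1 item 1.5.1 on this variable, and Appendix 2 already lists TEAEs by maximum dose separately.
- In SAP 7.4.3, delete 'Maximum' from the heading, since no such analysis is defined, and reconcile the section with the each-dose-level wording in Appendix 1 items 1.3 and 10.3.
- Keep the treatment-sequence analysis (7.4.2), the initial-dose analysis (7.4.3) and the dose-escalation analysis (7.4.4). The parent-study sequences should not replace the other two: they were fixed before RAJ2 outcomes, but they are not RAJ2 dose groups, because every RAJ3 or RAJ4 subject starts at 100 mg.
- If the ACR20 table is kept, footnote it as conditioned on response to the lower dose and not a dose comparison, and add it to item 1.5.1.

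The cost is SAP wording and the loss of one descriptive efficacy table. No data collection changes.
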